### 5.5.3 Vital Signs

Vital signs (systolic and diastolic blood pressure as well as heart rate) will be measured twice: after 5 minutes supine rest and after 2 minutes in standing position (one set of supine and standing vital signs) at visits VS1, VR, V1B, V1C, V2B, V2C, and V3B/EDV.

At VR, V1C and V2C three sets of supine and standing vital signs will be measured with 15-20 min intervals between the sets.

Vital signs’ parameters will be summarised using the mean value at each visit. The mean will be calculated if there is at least one non-missing value for a given parameter.

Results for systolic blood pressure, diastolic blood pressure, and heart rate will be classified according to whether the value was lower than (L), within (N) or higher than (H) the reference range for that parameter. The normal ranges are provided in Table .

**Table 6: Normal Ranges for Vital Signs**

Parameter	Lower Reference Range	Upper Reference Range
Systolic blood pressure – Supine [mmHg]	90	140
Diastolic blood pressure – Supine [mmHg]	60	90
Systolic blood pressure – Standing [mmHg]	80	140
Diastolic blood pressure – Standing [mmHg]	60	90
Heart rate [bpm]	50	100

The following tables and listings will be provided:

Table 15.2.5.1.T Summary of Vital Signs – Safety

Vital signs’ parameters will be summarised including change from baseline at each visit.

Table 15.2.5.2.T Incidence of Vital Signs Abnormalities – Safety

Number and percentage of subjects will be displayed in Low, Normal and High categories for every vital signs’ parameter. Percentage will be based on the number of subjects at specified visit.

#### Table 15.2.5.3.T Shift Table of Vital Signs Abnormalities – Safety

Shift tables showing changes in the number and frequency of subjects with respect to the normal range between baseline and endpoint will be provided. Subjects with missing data will be presented as part of a “missing” category.

#### Listing 16.2.8.1 Vital Signs – Enrolled

### **5.5.4 12-Lead Electrocardiogram (ECG) Data**

A 12-lead electrocardiogram (ECG) will be recorded after 10 minutes in supine position at visits VS1, VR, V1B, V1C, V2B, V2C, and V3B/EDV. The following ECG parameters will be collected:

- Heart rate (bpm)
- R-R interval (ms)
- PR interval (ms)
- QRS duration (ms)
- QT interval (ms)
- QT interval – Bazett correction (ms)
- QT interval – Fridericia correction (ms)
- Mean electrical axis (degrees)
- ECG diagnosis
- ECG abnormality assessment
- Comparison to baseline

ECG abnormality assessments of “Incomplete Analysis” and “Uninterpretable” will be considered as part of the “Not Applicable” category in summaries.

The central ECG reading provider will also assess the ECG results against baseline, using the following categories:

- Improved
- Unchanged
- Worsened
- Not Applicable
- Not compared

The clinical significance of ECG abnormalities will be additionally assessed by the investigator. If the assessment of clinical significance differs between the investigator and the ECG reading provider, the investigator’s assessment will be used in the analysis.

The following tables and listing will be presented:

#### Table 15.2.6.1.T Summary of ECG Parameters – Safety

ECG parameters will be summarised using default summary statistics including change from baseline at each visit.

#### Table 15.2.6.2.T Summary of ECG Diagnoses – Safety

The number and percentage of subjects with each ECG diagnosis will be displayed at each visit. Percentage will be based on the number of subjects at specified visit.

#### Table 15.2.6.3.T Summary of ECG Abnormality Assessments – Safety

Number and percentage of subjects with normal, abnormal, and CS abnormal ECG assessments will be displayed. Percentage will be based on the number of subjects at specified visit.

#### Table 15.2.6.4.T Shift Table of ECG Abnormality Assessments – Safety

Number and percentage of subjects with normal, abnormal, and CS abnormal ECG assessments will be displayed. Percentage will be based on the number of subjects at specified visit.

#### Listing 16.2.8.2 Electrocardiogram – Enrolled

### 5.5.5 Columbia-Suicide Severity Rating Scale (C-SSRS)

The C-SSRS is a tool that was developed to facilitate a prospective, systematic monitoring for the emergence of suicidal tendencies in clinical studies. It is used to compare the occurrence, severity, and frequency of suicide-related thoughts and behaviours during treatment in a clinical trial.

The C-SSRS Screening version will be used at VS1 to obtain baseline data, and the C-SSRS Since Last Visit version will be used to capture changes in the subject's status at visits VR, V1B, V1C, V2B, V2C, and V3B/EDV.

The following table and listing will be presented:

#### Table 15.2.7.T Summary of Columbia-Suicide Severity Rating Scale – Safety

Number and percentage of subjects with suicidal ideation and suicidal behaviour will be summarised using standard frequency tabulations at every visit. Percentage will be based on the number of subjects at specified visit.

#### Listing 16.2.8.3 Columbia-Suicide Severity Rating Scale – Enrolled

### 5.5.6 Movement Disorder Society-Sponsored Version of Unified Parkinson's Disease Rating Scale (MDS-UPDRS)

An MDS-UPDRS questionnaire is administered on visits VR, V1B, V2B, and V3B/EDV. The MDS-UPDRS consists of four parts:

1. Non-motor aspects of experiences of daily living (13 items)
2. Motor aspects of experiences of daily living (13 items)
3. Motor examination (33 scores based on 18 items)
4. Motor complications (6 items)

with each item being scored using an integer rating of 0 to 4.

A score will be calculated for each part of the MDS-UPDRS as the sum of all items in that part of the questionnaire. According to Goetz et al. [5], a valid score for the MDS-UPDRS parts can be calculated if the respective part contains a number of missing values less than or equal to the following:

- Non-motor aspects of experiences of daily living – 1
- Motor aspects of experiences of daily living – 1
- Motor examination – 3
- Motor complications – 0

For subjects with partially missing data, a prorated score will be calculated by taking the sum of all non-missing items, dividing it by the number of non-missing items, and multiplying it by the total number of items in each part. The prorated score will be rounded to the nearest whole number.

The total MDS-UPDRS score will be calculated as the sum of the scores of each part. The total score will not be calculated if the score for any part of the MDS-UPDRS is missing.

The following table and listing will be presented:

#### Table 15.2.8.T Summary of MDS-UPDRS – Safety

Each part of the MDS-UPDRS as well as the total score will be summarised at baseline, and at the end of each treatment period using default summary statistics.

#### Listing 16.2.8.4 MDS-UPDRS Questionnaire – Enrolled

### 5.5.7 Questionnaire for Impulsive-Compulsive Disorders in Parkinson's Disease – Rating Scale (QUIP-RS)

The Questionnaire for Impulsive-Compulsive Disorders in Parkinson's Disease – Rating Scale (QUIP-RS) is a tool designed to measure the severity of symptoms of impulse control disorders (ICDs) and related disorders. Subjects will complete the QUIP-RS at baseline (visit VR) and at the end of each treatment period (V1B, V2B, V3B/EDV).

The QUIP-RS consists of four primary questions, each applied to four ICDs (compulsive gambling, buying, eating and sexual behaviour) and three related disorders (medication use, punning and hobbyism). The QUIP-RS uses a 5-point scale (score 0-4 for each question) to rate the severity of each symptom based on its weekly frequency. The total ICD score ranges from 0 to 64, and the total QUIP-RS score for all ICDs and related disorders ranges from 0 to 112.

The following tables and listing will be presented:

Table 15.2.9.1.T Summary of QUIP-RS Items – Safety

Each part of the QUIP-RS will be summarised at baseline and at the end of each treatment period using default frequency tabulations.

Table 15.2.9.2.T Summary of QUIP-RS Scores – Safety

The total ICD score and total QUIP-RS score will be summarised at baseline and at the end of each treatment period using default summary statistics.

Listing 16.2.8.5 QUIP-RS Questionnaire – Enrolled

### **5.5.8 Physical Examination Findings**

Physical examinations will be performed at visits VS1, VR, V1B, V2B, and V3B/EDV on the following body systems:

- Head
- Neck
- Eyes
- Ear-nose-throat
- Heart
- Respiratory
- Gastrointestinal
- Hepatic
- Urogenital
- Musculoskeletal
- Vascular
- Lymphatic
- Dermatologic
- Central-nervous system (CNS)
- Psychiatric

Clinical significance (yes/no) of any abnormal physical examination findings will be assessed by the investigator.

Physical measurements (height, weight, and BMI) of subjects will be performed at VS1. In addition, weight and BMI will be repeatedly assessed at visits VR, V1B, V2B, and V3B/EDV.

The following tables and listings will be presented:

Table 15.2.10.1.T Summary of Physical Measurements – Safety

Physical measurement parameters will be summarised using standard summary statistics including change from baseline at each visit.

Table 15.2.10.2.T Summary of Physical Examination Findings – Safety

Number and percentage of subjects with normal, abnormal, and CS abnormal physical examinations findings will be displayed at each visit. Percentage will be based on the number of subjects at specified visit.

Listing 16.2.8.6 Physical Measurements – Enrolled

Listing 16.2.8.7 Physical Examinations – Enrolled

## 5.5.9 Other Safety-Related Observations

### 5.5.9.1 Pregnancy Testing

On visits VS1, VR, V1B, V2B, and V3B/EDV, female subjects of childbearing potential will undergo urine pregnancy testing. Pregnancy test results will be assessed as “positive” or “negative” by the investigator.

The following listing will be provided:

#### Listing 16.2.8.8 Pregnancy Testing – Enrolled

Childbearing potential and pregnancy test data will be listed for each female in the enrolled analysis set.

### 5.5.9.2 Safety Laboratory Screening

During VS1, certain safety laboratory parameters will be assessed for the purposes of subject eligibility screening. The following serology parameters will be collected:

- HAV-AB (IgM) (Hepatitis A)
- HBsAg (Hepatitis B)
- HCV-AB (Hepatitis C)
- HIV-Ag/Ab (HIV)

Each serology parameter will be assessed as positive or negative.

Additionally, blood coagulation will be assessed using prothrombin time (PT), and renal impairment will be assessed using glomerular filtration rate (GFR).

The following listing will be provided:

#### Listing 16.2.8.9 Safety Laboratory Screening – Enrolled

Safety laboratory data collected for screening purposes will be listed for subjects in the enrolled analysis set.

## 5.6 Efficacy Analysis

Efficacy will be assessed by evaluation of the following variables:

- Epworth Sleepiness Scale (ESS) score change from baseline at the end of each treatment period
- ESS score responder rate at the end of each treatment period
- Absence of residual somnolence at the end of each treatment period
- Psychomotor Vigilance Test (PVT) variable change from baseline at the end of each treatment period
- Montreal Cognitive Assessment (MoCA) score change from baseline at the end of each treatment period
- Actimetry change from baseline at the end of each treatment period
- Number and duration of diurnal involuntary sleep attacks (subject diaries) change from baseline at the end of each treatment period
- Episodes of somnolence (subject diaries) change from baseline at the end of each treatment period

The Full Analysis set as well as the Per Protocol set will be used for the analysis of efficacy data.

**Treatment periods** will be considered as evaluable for efficacy analysis only if the following rules are satisfied:

- IMP is taken for at least 7 days during the treatment period
- Last IMP intake is at most 3 days before the corresponding end-of-treatment visit, i.e. a maximum of 3 IMP intakes can be missed leading up to the end-of-treatment visit.

**Washout periods** will be considered as evaluable for efficacy analysis only if the preceding treatment period is evaluable and the last IMP intake is 6 or more days before the corresponding end-of-washout visit.

For the purposes of these rules, EDVs are considered as end-of-treatment (if the preceding scheduled visit was VR/V1C/V2C) or end-of-washout (if the preceding scheduled visit was V1B/V2B) visits.

A trial period not being evaluable for efficacy analysis according to these rules is considered a major protocol deviation.

Efficacy analyses for the FAS will be performed using data available from all scheduled visits, as well as EDV visits satisfying the above criteria. Efficacy analyses for the PP will be performed using only data from trial periods unaffected by major protocol deviations.

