8.2. Trial Populations

- The Safety Set (SS) includes all subjects who have received IMP at least once.
- The Full Analysis Set (FAS) includes all randomised subjects with an evaluable ESS score at the end of at least one treatment period. The efficacy analyses will be conducted on the FAS.
- The Per Protocol (PP) set includes all subjects who have completed the trial without major protocol deviation. Major and minor violations will be defined in the SAP. The main secondary endpoints (ESS, PVT and cognition) will be analysed with the PP set to demonstrate robustness of the primary analysis.

- The PK analysis set will include all subjects who have received treatment as per protocol (even if the trial was not completed) and who present no major protocol deviations with an impact on PK.

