8.3.1. Efficacy

Continuous efficacy endpoints – the change from baseline at each key visit (end of treatment period I, II, and III) in ESS, PVT and MoCA - will be analysed using a mixed linear regression model. The model will include the treatment, period, treatment by period interaction, sequence, and baseline scores as fixed effects, and the subject nested within sequence as a random effect.

Categorical efficacy endpoints – absence of residual somnolence and ESS responder status at each key visit – will be analysed using a mixed effects logistic regression model, with the treatment, period, treatment by period interaction, sequence, and baseline scores as fixed effects, and the subject nested within sequence as a random effect.

Treatment least square means and mean differences will be reported with their standard errors and 95% confidence intervals. The significance of the differences between Treatment A (THN102 Placebo), Treatment B (THN102 200/2) and Treatment C (THN102 200/18) will be assessed with a contrast t-test at the two-sided 5% level.

Handling of missing values/censoring/discontinuations: Subjects who misused their planned treatments or doses or have missing outcome measurements will not be excluded from the primary analysis in the FAS. Under the assumption that outcomes are missing at random, the mixed-model can propagate uncertainty due to missing data into estimates of treatment efficacy and other quantities of interest. Hence, missing data will not be imputed or replaced prior to the analysis.

Supportive analysis: The same analysis will be repeated on the PP set, to assess robustness of the analysis of the variables from ESS and PVT and possibly on other efficacy results. Subgroup analyses may be performed to investigate the effect of the main demographics (age, gender) and disease characteristics (in term of daily sleepiness extent, and cognitive impairment) on the efficacy outcomes.

The presence of a significant treatment by period interaction term in the main model may indicate a residual treatment (carryover) effect. In case of a significant treatment by period interaction, period I results will be analysed separately, and further analyses will be performed to explore the carry-over effects. The methods for evaluation of carryover effects will be defined in the SAP.

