## 3. ANALYSIS SETS AND SUBGROUPS

### 3.1 Analysis sets

The **Enrolled Set (ES)** includes all subjects who have signed the informed consent form.

The **Randomised Set (RS)** includes all subjects randomised at visit VR.

The **Safety Set (SS)** includes all subjects with at least one IMP administration.

The **Full Analysis Set** (FAS) includes all randomised subjects with an evaluable ESS score at the end of at least one treatment period. Evaluability of treatment periods is described in Section 5.6. The efficacy analyses will be conducted on the FAS.

The **Per Protocol** (PP) set includes all subjects in the FAS who have at least one treatment period without a major protocol deviation. Major and minor violations are defined in Sections 5.1.2 and 5.6. The main secondary endpoints (ESS, PVT and cognition) will be analysed with the PP set to demonstrate robustness of the primary analysis.

The **PK analysis set** will include all subjects who have received treatment as per protocol (even if the trial was not completed) and who present no major protocol deviations with an impact on PK.

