## 5.1.2 Protocol Deviations

All analysis sets are defined in Section **Error! Reference source not found.**. The per protocol (PP) set is defined as all subjects who have completed the trial without major protocol deviation.

During the Blind Data Review (BDR) the eligibility of subjects for the PP set will be assessed. The BDR will be performed after data entry, prior to locking the database. All decisions made during the BDR will be documented in the BDR report before the closure of the database.

Protocol deviations are deviations from the procedures outlined in the clinical trial protocol or from subsequent protocol-related instructions like missed evaluations, incorrect timing of evaluations, non-compliance with the IMP, intake of prohibited medications or any non-adherence to the clinical trial protocol that impacts subject's rights, safety or welfare. Protocol deviations that may affect the efficacy or PK outcome will be discussed during the BDR.

An appropriate clinical trial team, including a physician, will review potential protocol deviations and relevant information regarding those deviations to determine a possible impact on safety or efficacy endpoints. A decision will be made as to the effect of the possible deviations to determine if it is considered major or minor. The status, major or minor, of each protocol deviation will be documented in the BDR report. A subject may have one or more major protocol deviations resulting in the exclusion of that subject from the per protocol analysis set.

Reference listings will also be made available to help with the review of the protocol deviations.

Note: Protocol deviations will, if possible, be validated against data recorded in the eCRF. Note where an answer for an inclusion/exclusion tick box differs from the algorithmic check of the criteria, the algorithmic check will overrule the tick box.

Protocol deviations of the following categories and respective data listings will be reviewed during the BDR.

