**Additional trial conduct deviations**

No.	Deviation	Major/ Minor/ Case by case review
PD#25.	IMP treatment compliance according to eCRF or diary <80% or >120%, by treatment period and overall	case by case
PD#26.	IMP repeatedly taken not according to schedule (earlier than 7:00 or later than 9:00)	case by case
PD#27.	Duration of treatment and washout periods	case by case
PD#28.	IMP intake deviations related to PK analysis	case by case
PD#29.	Intake of prohibited medications	case by case
PD#30.	Adverse events that may significantly affect the key efficacy or PK trial endpoints	case by case
PD#31.	PDs from the global Protocol deviations log that may significantly affect the key efficacy or PK endpoints and are not covered by other listings	case by case

The specific content and format of listings to be reviewed during the BDR meeting (including any additional requirements that may be necessary to aid in review) will be determined outside the scope of this SAP.

Additional protocol deviation criteria were defined during the BDR meeting held on 10-FEB-2020. These deviations are described in full in the BDRM report (version Final 1.0, 20-FEB-2020). For a description of the rules and how they apply to efficacy and pharmacokinetic analysis, see Section 5.6 and Section 5.7 respectively.

The following tables and listing will be provided:

Table 15.1.6.1.S Major Protocol Deviations – Safety

Table 15.1.6.2.S Major Protocol Deviations – Full Analysis

Number and percentage of subjects with major protocol deviations will be summarised by affected trial period and overall. The categories of major protocol deviations will be included. Percentage will be based on the number of subjects in the respective analysis set.

Listing 16.2.2.1 Major Protocol Deviations – Safety

Major protocol deviations will be listed including the affected trial periods.

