### 5.6.1 Key Efficacy Analysis

On visits VS1, VR, V1B, V1C, V2B, V2C, and V3B/EDV subjects will fill out the Epworth Sleepiness Scale (ESS) questionnaire. The ESS consists of 8 questions with the answers on the scale of 0-3. The ESS score is the sum of the 8 items and has a range of 0-24. The **key efficacy variable** in this trial is the change from baseline of the ESS score at the end of each treatment period (visits V1B, V2B, and V3B/EDV).

The ESS score change from baseline will be analysed using a mixed linear regression model with the fixed effects of treatment, period, treatment by period interaction, sequence, and baseline score, and subject nested within sequence as a random effect. The model will be estimated using the restricted maximum likelihood method (REML). Degrees of freedom for the fixed effects will be estimated using the Kenward-Roger approximation.

The following SAS code will be used in mixed linear regression modelling:

```
PROC MIXED DATA=<Dataset> METHOD=REML;  
  CLASS <Subject> <Treatment> <Period> <Sequence>;  
  MODEL <Change from Baseline> = <Treatment> | <Period>  
      <Sequence> <Baseline>  
      / DDFM = KENROG;  
  RANDOM int / SUBJECT=<Subject>(<Sequence>);  
  LSMEANS <Treatment> / PDIFF CL;  
RUN;
```

A statistically significant (p-value < 0.05) treatment by period interaction may indicate the presence of residual treatment (carryover) effects, which may bias the estimates of treatment effects. For this reason, if a statistically significant treatment by period interaction is found in the analysis of the key efficacy endpoint, the key efficacy analyses will be performed using data from the first period only. In such an event, the key efficacy endpoint will be modelled using an analysis of covariance (ANCOVA) model with the fixed effect of treatment and baseline score as a covariate.

The following SAS code will be used in the analysis of first-period data:

```
PROC MIXED DATA=<Dataset> METHOD=REML;  
  CLASS <Treatment>;  
  MODEL <Change from Baseline> = <Treatment> <Baseline>  
      / DDFM = KENROG;  
  LSMEANS <Treatment> / PDIFF CL;  
RUN;
```

Additional exploratory analysis of the carryover effect is defined in section 5.6.2.

The following tables, listings and figures will be provided:

[Table 15.3.1.1.1.S Summary of Epworth Sleepiness Scale Score – Full Analysis](#)

[Table 15.3.1.1.2.S Summary of Epworth Sleepiness Scale Score – Per Protocol](#)

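### SAP 3.1 and 5.6 make FAS membership depend on drug intake, against the natural reading of Protocol 8.3.1 and without a declaration in SAP 7 (minor)

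*SAP*

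**What the plan says.** Protocol 8.2 defines the FAS as "all randomised subjects with an evaluable ESS score at the end of at least one treatment period". It does not say what makes a score evaluable and sets no intake threshold. Protocol 8.3.1, in its paragraph on missing values and discontinuations, adds: "Subjects who misused their planned treatments or doses or have missing outcome measurements will not be excluded from the primary analysis in the FAS".

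SAP 3.1 repeats the FAS definition and inserts one sentence: "Evaluability of treatment periods is described in Section 5.6". In SAP 5.6, treatment periods "will be considered as evaluable for efficacy analysis only if the following rules are satisfied". There are two rules: IMP on at least 7 days of the period, and a last intake no more than 3 days before the end-of-treatment visit. A period that fails is a major protocol deviation. The closing paragraph of 5.6 then says: "Efficacy analyses for the FAS will be performed using data available from all scheduled visits, as well as EDV visits satisfying the above criteria".

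If the treatment by period interaction is significant for ESS, SAP 5.6.1 says that "the key efficacy analyses will be performed using data from the first period only".

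The SAP discloses where the rules came from. Section 5.1.2 states: "Additional protocol deviation criteria were defined during the BDR meeting held on 10-FEB-2020", and refers to 5.6 for how they apply; the revision history says the same. SAP 7, which lists changes from the protocol, names only the change to the Per Protocol set.

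**The concern.** Taken together, SAP 3.1 and 5.6 turn an outcome-based membership condition into an intake-based one. A randomised subject who attends V1B, completes the ESS and has no qualifying period is outside the FAS. Since SAP 3.1 builds the PP set from the FAS, that subject is outside the PP set too, so no planned efficacy model contains the score.

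Stopping IMP can be a consequence of treatment. The adverse event data in SAP 5.5.1 record drug interruption separately from withdrawal, so a subject can be off drug and still attend a scheduled visit. Selecting subjects on intake after randomisation weakens the as-randomised comparison required by Protocol 8.3 and SAP 4.8.

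The rule is also uneven. Under the closing paragraph of 5.6, an off-drug V1B score from a FAS member is analysed. The same score from a subject with no other qualifying period is not. In the first-period fallback, whether a period I score counts can therefore depend on what happens in period II or III. That analysis has no within-subject control, so it is the one most exposed.

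**Working it through.** **The text, step by step.** Take a randomised subject with an ESS at the scheduled V1B, last IMP intake 5 days before that visit, and no later period.

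1. Protocol 8.2: an ESS at the end of a treatment period exists. No intake condition is stated.
2. Protocol 8.3.1: misuse of treatment does not exclude from the FAS analysis. The natural reading is that the subject is in.
3. SAP 5.6: 5 days is more than 3, so period I is not evaluable.
4. SAP 3.1: with no evaluable period, the subject is not in the FAS, and so not in the PP set.
5. SAP 5.6, closing paragraph: it selects records for FAS analyses. It does not restore membership.
6. SAP 7: no entry on the FAS.

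**The plan's own figure.** Protocol 8.5 gives 82% power for a paired t-test with n = 54, effect size 0.40 and two-sided alpha 0.05. The noncentral t with 53 degrees of freedom and noncentrality 0.40 × √54 = 2.94 gives 82.3%, so the figure reproduces.

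**Size in the mixed model.** The documents give no count of affected subjects, so these are assumptions:
- 54 completers, 9 per sequence.
- SD of a within-subject difference = 1, so residual variance 0.5. True dose C minus placebo difference 0.40.
- Intra-subject correlation ρ of 0.3, 0.5 or 0.7, giving between-subject variance 0.5ρ/(1 − ρ).
- The SAP 5.6.1 model by generalised least squares, with treatment, period, their interaction, sequence and random subject. The baseline covariate is left out.
- k extra subjects in sequences CAB or CBA with a V1B score only, each lacking the whole 0.40.

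Shrinkage of the dose C minus placebo estimate when the k subjects are included:

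| k | ρ = 0.3 | ρ = 0.5 | ρ = 0.7 |
|---|---|---|---|
| 1 | 0.0047 (1.2%) | 0.0034 (0.8%) | 0.0020 (0.5%) |
| 2 | 0.0093 (2.3%) | 0.0067 (1.7%) | 0.0040 (1.0%) |
| 3 | 0.0132 (3.3%) | 0.0094 (2.4%) | 0.0056 (1.4%) |

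Percentages are of 0.40. The standard error is about 1/√54 = 0.136, so the shifts run from 0.0020/0.136 = 1.5% to 0.0132/0.136 = 10% of one standard error. With one such subject on each of the three doses, the shift is 0.5% to 1.2%.

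**Size in the first-period fallback.** Each dose opens two of the six sequences, so 54/3 = 18 completers per dose. With k extra dose C subjects scoring as on placebo, the difference is 0.40 × 18/(18 + k), a shrinkage of k/(18 + k): 1/19 = 5.3%, 2/20 = 10.0%, 3/21 = 14.3%.

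**The case against.** The sponsor has a fair reply. The 8.3.1 sentence also covers subjects with missing outcome measurements, yet 8.2 leaves out anyone with no end-of-period ESS. The sentence therefore cannot override every membership condition and may be meant for subjects already in the FAS. The protocol leaves evaluability undefined and defers details to the SAP, so 5.6 could be called elaboration. This stands in part: the conflict is with the natural reading of 8.3.1, not with an unambiguous rule. But an intake-based definition does what that sentence appears to rule out, and SAP 7 is where a reader would look for it.

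The rules were set at a blind review and disclosed, so outcome-driven selection is not at issue. The exclusions would also be visible. Tables 15.1.1.1.S and 15.1.1.2.T give set counts by sequence and by treatment, Listing 16.2.3 gives reasons by subject, and Table 15.1.6.1.S gives major deviations by affected period. A reader might infer from Table 15.1.1.3, described without a treatment split, that an imbalance would be hidden; these other outputs show otherwise. They do not put the subjects into any efficacy model.

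A reader might also infer that 5.6 drops every non-qualifying period from the FAS model. Its opening words allow that, but the closing paragraph keeps all scheduled visits, SAP 4.6 attaches no intake condition to V1B, V2B or V3B, and SAP 5.1.2 describes the effect of major deviations on the PP set: "A subject may have one or more major protocol deviations resulting in the exclusion of that subject from the per protocol analysis set".

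**Conclusion.** The point holds as a minor one. SAP 3.1 and 5.6 remove from the FAS and the PP set a randomised subject whose scheduled ESS scores all come from non-qualifying periods. This sits badly with Protocol 8.3.1 and is not declared in SAP 7.

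The likely effect is small: about 0.5% to 3.3% of the dose C minus placebo estimate in the mixed model, and about 5% to 14% in the first-period analysis, which runs only after a significant interaction. Both ranges assume 1 to 3 affected subjects, all on dose C and all scoring as on placebo, which is a one-sided worst case. Efficacy is a secondary objective and SAP 2.6 calls the study exploratory.

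Two stronger readings are not supported. The gap between 60 randomised and 54 evaluable for efficacy in the synopsis might suggest a ceiling of 6 affected subjects. But Protocol 4.1 describes 54 as a target for subjects completing as per protocol, so it bounds nothing here. Nor does the rule for early discontinuation visits in SAP 4.6 and 5.6 breach the protocol, which sets no rule for using those scores in the model.

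**What to change.** Before unblinding:

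1. In SAP 3.1, define the FAS as all randomised subjects with an observed ESS, in at least one period, at a scheduled end-of-treatment visit or at an early discontinuation visit assigned to end of treatment under 4.6. Attach no intake condition to scheduled visits.
2. In SAP 5.6, state that every scheduled V1B, V2B or V3B score enters the FAS model as randomised, including the first-period analysis, and that for scheduled visits the 7-day and 3-day rules select PP periods only.
3. If the intake condition on FAS membership is kept instead, declare it in SAP 7 and add one run of the existing model that includes the removed subjects.

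The early discontinuation rule can stay as it is; a sensitivity run on it is optional. The cost is a few lines of SAP wording, plus one extra model run under option 3, with no new data. The FAS estimate may come out slightly smaller; the PP analysis still gives the on-drug estimate.
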